10 GROWTH OUTCOMES

10.1 Annualized HV

Descriptive statistics or HT will be presented. Annualized HV between two time intervals X and Y will be calculated as:

$$\begin{aligned} \text{Height Velocity} & \left(\frac{cm}{year}\right) \\ &= \left[\frac{\text{Month X Height (cm)} - \text{Reference Month Y Height (cm)}}{\text{Month X date} - \text{Reference Month Y date}}\right] * 365.25 \end{aligned}$$

HV will be calculated for the following intervals:

- 1. Periods III and IV
 - a. 12 month intervals, with the first 12 months starting with the first injection of Period III. Gaps in treatment will not alter that calculation of these 12 month intervals.
 - b. Last 6 and 12 month interval, using the last measure in Period IV with the measures at 6 and 12 months prior to the last measure as the reference.
- 2. Period V (PEN)
 - a. Intervals of 6 and 12 months from the start of the PEN injection as the reference for the first year.
 - b. After the first year of PEN, HV at the end of each year uses the measure at the Month 12 visit in each year with the measure at the Month 12 visit of the prior year as the reference. In cases where there is a gap in treatment between years, the measure at the restart of treatment (if available) will be used as the reference.

HV will also be presented for each treatment year, including Periods I and II, by the original treatment group assignment.

For patients who discontinue from the study between these specific defined visits for the calculations, their last HT measurement and date will be used for the annualized HV in the interval of interest.

Annualized HV by year, annualized HV on PEN treatment, change in HT SDS by year and change in HT SDS on PEN treatment will be summarized by ADA status.

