From the second year of the LT-OLE-PEN period and until marketing approval visits will be conducted every 3 months (months 3, 6, 9 and 12) ± 2 weeks, on day 4 (-1) post injection.

All visits assessments are detailed in section 5.4.2.

The investigator may conduct unscheduled visits, for safety reasons, or any other reason per investigator medical judgment.

Throughout the LT-OLE-PEN period, patients will continue to complete a patient diary at home to collect dosing and safety data.

Figure 1: Overall Study Design

* Patients from cohorts 1 and 2 who already started their second year of long term extension, will begin receiving 0.66 mg/kg/week as from their next scheduled visit

4. Study Population

In order to enroll up to 56 patients (allocated to 4 cohorts) into the Main Study, a sufficient number of pre-pubertal males aged 3 – 11 and females aged 3 – 10, with either isolated growth hormone deficiency (GHD) or GH insufficiency as a part of multiple pituitary hormone deficiency, will be recruited from 10 to 12 countries and 20 to 40 different centers. All centers will be specialized in the treatment and management of pediatric GHD.

The study population will consist of 2 subgroups:

1. Patients with peak GH level of [REDACTED] ng/ml (up to 40 patients).
2. Patients with peak GH level of [REDACTED] ng/ml and [REDACTED] ng/ml (up to 16 patients).

Patients must meet all of the inclusion and none of the exclusion criteria to be eligible. Patient eligibility will be verified by the study Medical Monitor before randomization.

OPKO Biologics	Protocol for Clinical Study CP-4-004	Page 41 of 133
Effective Date: Date of final electronic approval		

Patients who complete 12 months of treatment in the Main Study will be eligible to continue the treatment with MOD-4023 in a 12-month OLE period, and subsequent LT-OLE period and LT-OLE-PEN period until marketing approval in their country. The LT-OLE-PEN period will be extended on an annual basis until marketing approval in each country, subject to submission of an annual extension notification to the local EC/IRB.

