6 CONVENTION FOR REPORTING TREATMENT PERIODS

Periods III and IV: The protocol defines Period III as a 12 month period when patients are in three specific dose groups, and Period IV as starting on 0.66 mg/kg/week after 12 months in Period III. Because of the differences in timing of transition to the 0.66 mg/kg/week dose, all data from Periods III and IV will be presented in 12 month intervals, starting with the first dose of treatment at the start of Period III. The dose at the beginning of each 12 month period will be used to classify the patient to a dose group for disposition purposes. For the first 12 months, the results will be reported by the assigned dose group. After the initial year on OLE, all patient results will be summarized in a single treatment group, regardless of assigned dose level, or any individual patient dose adjustments.

Period V: This period will contain data from patients on PEN treatment. Baseline data for this period will be the data collected at the visit for the first PEN dose, prior to the first PEN dose.

The cumulative change in HT SDS from the start of treatment in Period I will also be summarized. For these summaries, the original dosing assignment will be used, and the reporting periods will be at each of the scheduled Month 12 visit of the period. Gaps in treatment will be included, so that the elapsed time may be longer than 12 months.

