7.4 Data Handling and Missing Data

Because of the observational nature of this study, missing data in general will not be imputed, except for:

1. specific items associated with AEs as specified in Section 9.1;

2. missing day or month will be imputed to the 1st of each if needed for calculations, unless this imputation contradicts a previous date (such as between start and stop dates). In this case, the imputed date will be last day or month, or be missing and presented as "ongoing."

Unscheduled assessments or multiple results within a specified visit window will be listed, but not used in the visit summary. The assessment closest to the scheduled visit date will be used.

Early termination assessments will be assigned to the appropriate annual interval based on treatment month within a period.

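### Annualized height velocity accepts a drop-out's last height over any interval, however short, into small yearly means; a lesser point is that tables joining OLE and PEN years treat treatment gaps in two ways

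*SAP*

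**What the plan says.** SAP 10.1 defines annualized height velocity (HV) as the height difference divided by the days between the two measurements, times 365.25. It contains three rules that matter here.

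- **Drop-outs, all periods:** "For patients who discontinue from the study between these specific defined visits for the calculations, their last HT measurement and date will be used". This value enters the yearly HV. SAP 7.4 adds: "Early termination assessments will be assigned to the appropriate annual interval based on treatment month within a period". Neither section sets a shortest permitted interval.
- **Gaps, Periods III and IV (item 1a):** "Gaps in treatment will not alter that calculation of these 12 month intervals". Off-treatment time after the first Period III injection stays in the velocity.
- **Gaps, Period V after the first PEN year (item 2b):** "In cases where there is a gap in treatment between years, the measure at the restart of treatment (if available) will be used". The velocity is then counted from that height, and off-treatment time between PEN years is left out. If there is no restart height, the previous Month 12 height remains the reference and the gap stays in.

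SAP 11.1 shows OLE and PEN years together in Tables 10, 14.2.1.3, 14.4.2.1 and 14.4.2.3. Tables 14.2.1.1 (OLE) and 14.2.1.2 (PEN) keep them apart. Growth is the secondary objective (SAP 3.1.2), and SAP 4.1 and 7.1 plan no hypothesis tests.

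**The concern.** **Main point.** An annualized value from a few weeks of growth is mostly scaled-up measurement error, yet it enters the yearly mean with the same weight as a full-year value. The groups are small: 53 children entered the OLE (SAP 4.1), split by three doses in OLE year 1 and by four initial cohorts in Table 14.2.1.3. Wherever the documents fix an interval for a growth rate, it is at least six months: inclusion criterion 5b, the growth-rate discontinuation rule for LT-OLE-PEN (Protocol 4.6), and the definition of final adult height (SAP 10.2). The drop-out rule is the exception.

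**Lesser point.** In a table with OLE and PEN years side by side, the same child with the same gap could show a lower velocity in an OLE year than in a later PEN year, if growth slows off treatment, purely because the reference height is chosen differently. The columns are then not strictly comparable.

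**Working it through.** The plan gives no figure on either point, so there is nothing to reproduce. The SAP 10.1 formula is applied directly.

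**Drop-out rule**

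Inputs: the factor 365.25/days from SAP 10.1, and 53 children from SAP 4.1. An even split is assumed, giving 53/3 = 17.7 (about 18) per dose group and 53/4 = 13.25 (about 13) per initial cohort. The documents give no between-visit height error, so 0.1 to 0.5 cm is assumed. The 0.5 cm end is the within-visit repeat limit in Protocol Appendix 9; it is an upper illustration, not a typical error.

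Error in one child's HV = height error × 365.25/days. Shift in the mean = that error / n.

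| Interval | Factor | HV error, 0.1 to 0.5 cm (cm/yr) | Shift, n = 18 | Shift, n = 13 |
|---|---|---|---|---|
| 30 days | 365.25/30 = 12.2 | 1.22 to 6.09 | 0.07 to 0.34 | 0.09 to 0.47 |
| 91 days | 365.25/91 = 4.0 | 0.40 to 2.01 | 0.02 to 0.11 | 0.03 to 0.15 |
| Six months | 365.25/182.6 = 2.0 | 0.20 to 1.00 | – | – |

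For a full year the factor is 1.0. For a Month 6 visit held two weeks early it is 365.25/168 = 2.2.

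Which row is realistic? Scheduled heights are mostly about three months apart, and the week-4 PEN visit takes no height (Protocol 5.4.1.2). A 30-day value therefore comes mainly from an early-termination visit, which follows the Month 12 assessments of the period (Protocol 5.5.2) and can fall at any time.

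**Gap rules**

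Inputs: a 60-day gap, chosen because Protocol Appendix 3 provides a follow-up visit for children off treatment for longer than that before LT-OLE. Growth of 6-10 cm/yr on treatment and 2-5 cm/yr off treatment is assumed. The documents give neither growth rates nor gap frequency.

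- Fixed 12-month window: lowering = (on − off) × 60/365.25, from 1 × 60/365.25 = 0.16 to 8 × 60/365.25 = 1.31 cm/yr.
- Window lengthened by the gap: (on − off) × 60/425.25, from 0.14 to 1.13 cm/yr.
- Under the restart rule the lowering is zero.
- Shift in a yearly mean if 10% of children had such a gap: 0.1 × (0.14 to 1.31) = 0.01 to 0.13 cm/yr. If 20%: 0.03 to 0.26.

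The top of each range pairs the fastest assumed growth on treatment with the slowest off it.

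Exposure is narrow. Gaps before the first Period III injection and before the first PEN dose fall outside both series. What remains is mainly the OLE-to-LT-OLE gap on one side and any between-year PEN gap on the other.

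**The case against.** The strongest reply is that these are disclosed, period-specific choices in a descriptive analysis. Much of it stands.

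- **Safeguards exist.** SAP 7.1 also reports the median, minimum and maximum; the median resists one outlier and the extremes expose it. SAP 9.13 promises a listing of treatment gaps, and Listing 16.2.6.1 gives HV by visit. These let a reader find an affected child, but they do not make the means stable or the columns comparable.
- **The six-month intervals cited govern decisions about one child,** not group tables. That is so; they show what the documents treat as a usable growth interval, and do not by themselves impose a rule on the tables.
- **A six-month minimum could select.** Protocol 4.6 allows discontinuation for unsatisfactory growth response in Periods I-IV and, in LT-OLE-PEN, at a growth-rate threshold. Leaving out short final intervals could remove slow growers and raise the mean. This stands, and it is why the restricted figure should not replace the all-inclusive one.
- **The choice of a single gap rule is largely preference.** A restart reference in every year would also be consistent. It often could not be calculated for the OLE-to-LT-OLE gap, because the tests listed for that return (Protocol 5.3; Appendix 3, Visit 0) include no height. For cumulative height SDS, SAP 6 already takes the inclusive route ("Gaps in treatment will be included, so that the elapsed time may be longer than 12 months"), although that is a different endpoint.

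A reader might also infer that SAP 7.4 makes a restart height unusable, since it says "Unscheduled assessments or multiple results within a specified visit window will be listed, but not used in the visit summary". The documents do not support this: the sentence governs which result enters a visit summary, while SAP 10.1 specifically directs use of a restart height.

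**Conclusion.** The point holds as a minor one.

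The drop-out rule lets a short-interval value into small yearly means with its error multiplied by about 4 at a three-month visit and about 12 at 30 days. For one child the shift is 0.02-0.15 cm/yr at 91 days and 0.07-0.47 at 30 days, across the two group sizes. This rests on assumed errors of 0.1-0.5 cm and an even split of the 53. The number of drop-outs, and the number remaining after OLE year 1, are not given.

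The two gap rules are a real inconsistency in the four combined tables, but the group effect is probably small and cannot be sized from the documents.

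Two stronger readings are tempting and not supported:

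- **That the yearly means are generally unreliable.** The larger shifts need a very early termination visit and the upper-end error. The reported height is the average of three readings (SAP 8.3), so 0.5 cm is unlikely to be typical.
- **That the plan biases the vial-versus-PEN comparison.** The drop-out rule applies alike in all periods. The gap rules differ only for some gaps. The separate OLE and PEN tables do not mix them, and item 1b adds a Period IV summary ("Last 6 and 12 month interval, using the last measure in Period IV with the measures at 6 and 12 months prior") that does not depend on PEN data.

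No test, error rate or primary objective is touched.

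**What to change.** **Drop-outs.** In the HV summaries, show two rows side by side, each with its n:

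1. HV limited to intervals of at least six months, counting a Month 6 visit within its window.
2. The SAP's current all-inclusive HV.

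State how many children are left out of the first row and why they discontinued, because their exclusion may be informative. Keep them in the listings and the height SDS summaries.

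**Gaps.** In Tables 10, 14.2.1.3, 14.4.2.1 and 14.4.2.3 and their matching figures only, compute all years on the gap-inclusive basis. In PEN years after the first, this means keeping the previous Month 12 height as the reference whether or not there was a gap. Retain the item 2b restart-referenced HV as a further row with its n, so that the SAP's present result is not lost. For this point Tables 14.2.1.1 and 14.2.1.2 stay as they are. Add a cross-reference to the gap listing in SAP 9.13.

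**Cost.** SAP wording and modest programming; no new data. The tables gain rows, the six-month row loses some n, and for PEN children with a between-year gap the gap-inclusive row will contain off-treatment time.

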10.2 Achievement of Final Adult Height

The number (and proportion) of patients who achieve adult height will be summarized by age. The denominator for proportion for this summary will be the total of patients in the study, so that patients who discontinue from the study are simply considered not to have achieved adult height. A Kaplan-Meier curve will be used to display the proportion of patients achieving adult height by age. For the Kaplan-Meier curve, discontinued patients will be censored, and removed from the denominator. Achievement of final adult height is defined as the HT when annualized HV < 1 cm/year over at least six-month period.

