1.1.1 Aetiology

Childhood GHD can be congenital, acquired, or idiopathic. Underlying causes of two of these three types of GHD in children have been identified:

- Congenital
 - Defective pituitary development that leads to pituitary aplasia
 - Empty sella

OPKO Biologics	Protocol for Clinical Study CP-4-004	Page 31 of 133
Effective Date: Date of final electronic approval		

- Encephalocoele
- Midline defects
- Septo-optic dysplasia
- Panhypopituitarism
- Genetic abnormalities; autosomal-recessive, autosomal-dominant, or X-linked defects or a mutation or deletion in the growth hormone gene or in the GHRH.
- Acquired
 - Tumours of the hypothalamic-pituitary region - Craniopharyngioma is the most common tumor
 - Cranial irradiation, surgical intervention
 - Infiltrative diseases, including sarcoidosis, tuberculosis, histiocytosis X, haemochromatosis, and lymphocytic hypophysitis
 - Trauma (specifically traumatic brain injury)
 - Hypoxic insult
- Idiopathic

In most cases, no clear aetiology can be identified.

The idiopathic origin of GHD is poorly understood but it appears to be multifactorial. Retrospective analyses have considered familial traits (such as parental height) and perinatal risk factors (such as gestational age and birth size and weight) as possible predictors. Similarly, correlates of idiopathic GHD with untoward events during pregnancy and complications during birth have been examined. There are non-random effects evident in the frequency of GHD (and multiple pituitary hormone deficiency) dependent on some of these apparently extraneous influences, notably traumatic birth experience. The evidence suggests a model of causality in which there are ill-defined underlying familial and gender (males predominate 3-4:1) predispositions which are exacerbated by early life "adverse" events and result in deficiency, the degree of which (isolated GHD or multiple pituitary hormone deficiency) is determined by the severity of the "adverse" early life event.

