4.1 INCLUSION CRITERIA

1. Pre-pubertal child aged \geq 3 years old and not above 10 years for girls or 11 years for boys, with either isolated GHD, or GH insufficiency as part of multiple pituitary hormone deficiency.
2. Confirmed diagnosis of GHD by two different GH provocation tests defined as a peak plasma GH level of █ ng/ml¹, determined by central laboratory using a validated assay². If the patient has already been tested locally and reserve samples that were taken at appropriate time-points are available, these will be reanalyzed by the central laboratory³. Historical tests missing the -30 minutes time point will be accepted. If no reserve samples are kept (only for tests performed prior to site initiation), then the details of the locally performed tests will be reviewed by the Coordinating Investigator: if the results cannot be accepted, the patient will undergo both stimulation tests during the screening period and the samples will be analyzed by the central laboratory. At least one of the two stimulation tests (and preferably both) will be analyzed by the central laboratory. If the patient requires sex hormone priming (due to the age), and both stimulation tests must be performed during the Screening (no historical samples kept, or test was without priming), it is recommended to perform stimulation tests in consecutive setting in one day, or in two consecutive days, to avoid priming the patient twice. Local historical tests without sex-steroid priming will not be accepted for patients that require sex steroid priming according to the protocol.
3. Bone age (BA) must be not older than chronological age, and should be no greater than 9 years for girls and 10 years for boys.
4. Without prior exposure to any r-hGH therapy.
5. Impaired height and height velocity defined as:
 - a. Height (HT) of at least 2.0 standard deviations (SD) below the mean height for chronological age (CA) and gender according to the standards of Prader et al. (1989) (HT SDS \leq -2.0);
 - b. Annualized height velocity (HV) below the 25th percentile for CA (HV $<$ -0.7 SDS) and gender according to the standards of Prader et al. (1989). The interval

¹ Patients will be divided into two subgroups: Patients with peak serum GH levels after stimulation test █ ng/ml and patients with peak serum GH levels after stimulation test █ and █ ng/ml.

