4.1 Sample Size and Statistical Power Consideration

All patients who completed 12 months of treatment in the main study (Periods I and II) were eligible to enroll into the OLE (Periods III, IV, etc.). Fifty-three (53) patients completed Period II and started the OLE. There are no formal power considerations nor hypothesis tests for the OLE data.

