5 ANALYSIS POPULATIONS (ANALYSIS SETS)

Since this is an OLE with patients from the primary study, all patients will be included in a single Full Analysis Set for reporting.

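### SAP 10.2 shows adult-height attainment by raw age with no split by sex; if girls reach the endpoint earlier, the Kaplan-Meier curve and the by-age proportion are both sex mixtures

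*SAP*

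**What the plan says.** SAP 10.2 plans two outputs on adult height. The first is a summary: "The number (and proportion) of patients who achieve adult height will be summarized by age". Its denominator is every patient in the study, and those who discontinue count as not having reached adult height. The second is a curve: "A Kaplan-Meier curve will be used to display the proportion of patients achieving adult height by age". Here the handling differs: "For the Kaplan-Meier curve, discontinued patients will be censored, and removed from the denominator". The event is the same for both sexes: "Achievement of final adult height is defined as the HT when annualized HV < 1 cm/year over at least six-month period".

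The section mentions no split by sex, and the rest of the SAP does not supply one. Section 5 says that "all patients will be included in a single Full Analysis Set for reporting". Section 4.1 gives the number: "Fifty-three (53) patients completed Period II and started the OLE". Sections 10.1 and 10.3 break growth outcomes down by year, original treatment group and antibody status only. Sections 11.1 and 11.3 list no adult-height table and no Kaplan-Meier figure, pooled or by sex. Gender itself is available, since SAP 8.2 summarizes it with the demographics.

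**The concern.** The horizontal axis is chronological age, and the protocol repeatedly treats a given age as meaning different things in boys and girls. Its bone-age limit at entry, for example, "should be no greater than 9 years for girls and 10 years for boys". Protocol 5.6 standardizes height and height velocity for both age and gender. SAP 10.2 indexes a growth endpoint by raw age with neither a sex standard nor a sex split.

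If girls stop growing at younger ages, a single curve averages two curves that lie apart on the axis. Its value at any age then reflects how many boys and girls are in the sample as well as how early each sex reaches adult height. At stake is whether the output can be read for a boy or for a girl, or set beside a cohort with another sex ratio.

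**Working it through.** **No figure to reproduce.** The plan gives no expected age at adult height, event count or precision for this analysis.

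**Step 1: what the protocol says about sex and age.**

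| Limit | Girls | Boys | Gap | Place |
|---|---|---|---|---|
| Upper entry age | 10 | 11 | 1 year | Protocol 4.1, item 1 |
| Upper bone age at entry | 9 | 10 | 1 year | Protocol 4.1, item 3 |
| LH, FSH and sex-steroid testing starts | 12 | 13 | 1 year | Protocol 5.3 and 5.7.1.4 |
| Sex-hormone priming | over 8 | over 10 | 2 years | Protocol 5.1.1 |

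These concern eligibility and testing. They show the direction the plan assumes; they do not give an age at adult height. A gap of one to two years is therefore an assumption.

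**Step 2: the pooled value as a mixture.** With male share m, ignoring censoring:

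F(age) = m × F_boys(age) + (1 − m) × F_girls(age)

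Assumptions, none from the documents: normal ages at attainment, SD 1 year, boys' mean 16.5, girls' mean 15.5 or 14.5. The two values of m are 0.50 and 0.78. The latter is 3.5/4.5, the middle of the background remark in Protocol 1.1.1 that "males predominate 3-4:1".

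At 15.5 years, F_boys = Φ(−1) = 0.159, and F_girls = Φ(0) = 0.500 or Φ(1) = 0.841.

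- 1-year gap, m = 0.50: 0.50 × 0.159 + 0.50 × 0.500 = 0.33
- 1-year gap, m = 0.78: 0.78 × 0.159 + 0.22 × 0.500 = 0.23
- 2-year gap, m = 0.50: 0.50 × 0.159 + 0.50 × 0.841 = 0.50
- 2-year gap, m = 0.78: 0.78 × 0.159 + 0.22 × 0.841 = 0.31

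The sex mix alone moves the pooled value by about 10 points (1-year gap) or 19 points (2-year gap).

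**Step 3: sensitivity.** SD varied from 0.75 to 1.5 years, and m from 0.50 to 0.80.

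- 1-year gap: the pooled median lies 0.50 year after the girls' median at m = 0.50, and 0.81 to 0.83 year after it at m = 0.80. At the girls' median age, boys stand at 9-25%; the pooled value is 30-38% at m = 0.50 and 17-30% at m = 0.80.
- 2-year gap: the pooled median lies 1.00 year after the girls' median at m = 0.50, and 1.65 to 1.77 years after it at m = 0.80.

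In every case the pooled median falls between the sexes and matches neither.

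**Step 4: how the two outputs differ.** The by-age proportion has a fixed denominator, so its composition is the enrolled mix. The Kaplan-Meier curve uses a risk set that changes with age. A simulation of 200,000 patients shows the effect. It assumed half boys, girls' mean 15, boys' mean 16, SD 1, entry ages uniform over 3-10 for girls and 3-11 for boys, and censoring after a fixed follow-up. At age 15, where the uncensored mixture is 32.9%:

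| Follow-up | Boys' share of those at risk | Pooled Kaplan-Meier value |
|---|---|---|
| 5 years | 100% | 25.8% |
| 7 years | 69% | 31.4% |
| 9 years | 65% | 32.3% |

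With short follow-up, the pooled curve need not recover even the mixture.

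**Step 5: precision after a split.** The 95% half-width at the median without censoring is 1.96 × √(0.25/n). If 75-80% of the 53 are boys, there are about 40 to 42 boys and 11 to 13 girls. The half-width is 0.13 for n = 53, 0.15 for n = 40, 0.27 for n = 13 and 0.30 for n = 11.

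**The case against.** The case against giving this much weight is strong, and most of it stands.

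- **The limits are indirect evidence.** None states an age at adult height. A reader might infer that the protocol establishes a one-year gap in attainment; it does not, and its priming limits differ by two years.
- **The size is hypothetical.** The boys' mean, the SD and both sex mixes are assumed. The 3-4:1 ratio is background on idiopathic growth hormone deficiency, not the enrolled mix. A reader might take 10 to 19 points as an error in a planned result. It is the difference between two imagined cohorts; this study has one mix, which the documents do not report.
- **The curve is not the only output on adult height.** SAP 10.2 also plans the by-age proportion, and Listing 16.2.1.1c gives final height per patient. With the demographics listing, a reader could separate boys from girls by hand.
- **The by-age proportion does not follow a changing risk set.** It is tempting to say that both outputs shift with the patients still followed. That describes the curve only. Follow-up can alter the proportion's numerator, but the denominator is fixed.
- **The stakes are low.** Adult height is not among the growth outcomes in SAP 3.2.2, the extension has no hypothesis tests, and no comparison with another cohort is planned. A pooled curve is a legitimate description of the enrolled group.
- **Pooling is read from silence.** SAP 10.2 neither specifies nor excludes a split. Still, one curve for patients in one analysis set, with no sex-specific output listed, can only be taken as pooled.

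What survives is that no split is stated, the axis is raw age, and the protocol elsewhere takes care to treat that axis differently for girls and boys.

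**Conclusion.** The point holds as a minor improvement to a descriptive output. As written, SAP 10.2 yields a by-age proportion and a Kaplan-Meier curve for boys and girls together. If girls reach the endpoint one to two years earlier, both are mixtures. The proportion depends on the enrolled sex mix, and the curve depends also on the mix of those still at risk at each age.

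The illustrative spread at 15.5 years (16% in boys, 50-84% in girls, 23-50% pooled) shows that the effect could be large enough to mislead a reader of the curve. It rests wholly on the assumed means, SD and sex mixes. The documents do not support a claim that a stated result is wrong, that a test or error rate is affected, or that adult height cannot be examined by any other route.

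**What to change.** In SAP 10.2, state that the Kaplan-Meier curve and the by-age count and proportion will be presented separately for boys and girls, with numbers at risk under the curve, and keep the pooled version as a secondary display. Add these outputs to the lists in SAP 11.1 and 11.3, where no adult-height table or curve now appears.

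No new data are needed. The change is a sentence or two in the text, a strata option in the program and the added list entries. The real cost is imprecision in the smaller group (Step 5), which will be greater once patients are censored and could be severe if few reach adult height during follow-up. Showing the numbers at risk makes this visible.
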